# 4.5 Rationale for Study Design

Oxymetazoline has been shown in 3 pivotal Phase 3 studies to be effective in treating persistent facial erythema in subjects with rosacea. Energy-based therapies have also been seen to be efficacious in reducing erythema and telangiectasia in rosacea patients. This Phase 4 study is the first to investigate the safety, tolerability, and preliminary measurements of oxymetazoline HCl cream 1.0% when used as an adjunctive treatment to energy-based therapy (ie, KTP, IPL, and PDL) for patients with moderate to severe persistent facial erythema associated with rosacea.

The side effects of energy-based therapy can include transient pupura and immediate posttreatment erythema, which normally resolve within a day or 2. In a recent publication, energybased therapy was performed the same day as Mirvaso® application for the treatment of rosacea with no safety concerns reported related to concurrent treatment. As an additional safety precaution we are delaying oxymetazoline treatment for 48 hours post energy-based therapy (and 24 hours prior to re-treatment with energy-based device) to limit any potential interaction between the device and drug. Any potential AEs that may arise from the use of a device will be noticeable within a 48-hour window, which will alert the physician as to whether oxymetazoline treatment should be applied.

There are 6 safety determinations in the current study (adverse events, urine pregnancy in females of childbearing potential, physical examination, vital signs, Clinician's Telangiectasia Assessment [CTA], and Dermal Tolerability Assessment). Four assessments will be used as measures of efficacy: Clinician Erythema Assessment [CEA], Items from Satisfaction Assessment for Rosacea Facial Redness, FACE-Q Satisfaction with Skin Scale, and Digital Image Analysis [DIA] of standardized photography of the treatment area).

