### 5 STUDY ENDPOINTS

### 5.1 Primary Endpoints

The primary endpoints of the study are:

- The incidence of treatment emergent adverse events (TEAEs) and serious adverse events (SAEs).
- The number and percent of subjects with at least a 1-grade worsening from baseline in the Dermal Tolerability Assessment at any timepoint over the treatment period.
- The number and percentage of subjects with at least a 1-grade worsening from baseline in the CTA at any timepoint over the treatment period.

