# 5.6 Investigational Products and Therapies

# 5.6.1 Investigational Products Administered

Oxymetazoline HCl cream 1.0% will be applied in a thin layer topically to the entire face including forehead, nose, each cheek, and chin, once daily. Subjects will be instructed to apply study drug to their clean, dry face in the morning, at approximately the same time each day, starting on Day 3 through Day 56. There will be a 3 day washout period from the study drug beginning 24 hours prior to the second energy-based therapy session on Day 29 (subjects will not apply the study drug on Day 28, Day 29, and Day 30) to ensure that energy-based therapy and treatment with oxymetazoline are clearly separated in the case of any treatment-related adverse events. The Investigator should assess if any adverse events resulting from treatment with the energy-based device (eg, treatment site skin irritation or wounding) would present a risk for treatment with oxymetazoline and either delay or discontinue treatment.

For study visits, subjects will be instructed to apply the study drug at the study site. The dose will be applied after predose study assessments and procedures are completed. Site personnel

Allergan		06 Feb 2018
CMO-MA-MED-0530	Version 2	Page 22 of 59

will observe subject dosing in the clinic to ensure proper study drug application technique and retrain if necessary. Detailed instructions on study drug application will be provided to subjects (see Section 5.6.12).

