#### Documentation and Reporting of Adverse Events

Adverse events should be reported and documented in accordance with the procedures outlined below. All AEs occurring during the study must be documented on the relevant eCRF pages. The following data should be documented for each AE:

- Description of the symptom event
- Classification of 'serious' or 'not serious'
- Severity
- Date of first occurrence and date of resolution (if applicable)
- Action taken
- Causal relationship
- Outcome of event (unknown, recovered, not yet recovered, recovered with sequelae, death [with date and cause reported])

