6.2 Adverse Events

Adverse events will be coded using MedDRA version 20.1 or later to give a PT and a SOC term for each event.

An adverse event (AE) is defined as any untoward medical occurrence in a clinical investigational patient administered a pharmaceutical (investigational) product and which does not necessarily have to have a causal relationship with this treatment.

All AEs will be included in by-subject AE listings. A separate listing will be created with all the distinct levels of SOC and PT, and the verbatim investigator description reported in the study. Sorting will be by earliest observed SOC, PT within SOC and then verbatim description.

A treatment-emergent adverse event (TEAE) is a post-baseline AE where (i) there is no pretreatment AE of the same MedDRA primary SOC and PT; or (ii) the maximum severity during the post-baseline period is greater than the maximal severity of any pre-treatment AE of the same MedDRA primary SOC and PT during the screening/baseline period. Note that the post-baseline period of the study starts upon the initiation of the energy-based therapy at Day 1.

Any AEs reported after signing of the Informed Consent Form and prior to the energy-based therapy on Day 1 are considered pretreatment AEs (PTAEs)

Relationship to study drug is categorized as 'related', 'possibly related', 'unlikely related', 'not related', and 'not assessable'. Relationship to trial medication as per investigator is not expected to be missing after data cleaning. However, if relationship is confirmed as missing, the AE will be considered as treatment related as per PI.

An overall summary of frequency count and the binomial incidence proportion with associated 95% CIs will be presented to describe the incidents of TEAEs. Note that 95% CIs of the binomial incidence proportion will be presented for the overall summary analyses of TEAEs, but not for the by-visit/timepoint analyses. Percentages and corresponding 95% CIs will be displayed to 1 decimal place.

Each type of AE will be tabulated by SOC and PT within SOC. The SOC and PT within SOC will be sorted by descending frequency. If a subject has multiple occurrences (start and stop) of an event associated with a specific SOC and PT, a patient will only be counted once in the incidence count for the SOC level and once at each PT within the SOC level.

The incidence of all TEAEs by SOC and PT will be presented for the following categories:

• Any TEAE

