• Any TEAE related to energy-based therapy and leading to discontinuation of study medication

• Any TEAE related to treatment (i.e., study medication or energy-based therapy or both)

- Any TEAE by maximum severity
- Any PTAE

The following listings will be provided:

- Listing of all TEAE
- Listing of patients with TEAEs related to energy-based therapy and leading to discontinuation of study medication
- Listing of patients with TEAEs leading to discontinuation of treatment

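### The listed TEAE and SAE tables do not separate events by onset window or by drug versus device, although the protocol spaces cream and energy sessions so that treatment-related events can be told apart

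*SAP*

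**What the plan says.** - **Endpoint.** The first primary endpoint in Protocol 5.1 is "The incidence of treatment emergent adverse events (TEAEs) and serious adverse events (SAEs", with no split by source or timing.
- **Start of counting.** SAP 6.2: "Note that the post-baseline period of the study starts upon the initiation of the energy-based therapy at Day 1". The first cream application is on Day 3.
- **Purpose of the spacing.** Protocol 5.6.1 leaves out the cream on Days 28 to 30 "to ensure that energy-based therapy and treatment with oxymetazoline are clearly separated in the case of any treatment-related adverse events". Protocol 4.5 adds: "Any potential AEs that may arise from the use of a device will be noticeable within a 48-hour window".
- **Expected device effects.** Protocol 4.5: "The side effects of energy-based therapy can include transient pupura and immediate posttreatment erythema". No rate is given.
- **Tables.** SAP 6.2 lists TEAE tables by SOC and PT. Its only table of all related TEAEs is "Any TEAE related to treatment (i.e., study medication or energy-based therapy or both". One table concerns energy-based therapy alone, but it is restricted to events that led to stopping study medication. SAP 6.3 has the same structure for SAEs. SAP 6.8 plans no safety subgroups.
- **Causality.** Protocol 7.1.2.1 (Assessment of Causality) and SAP 6.2 both define categories of relationship to study drug only.
- **Onset.** The AE data items in Protocol 7.1.2.1 include "Date of first occurrence and date of resolution (if applicable", with no time of day.

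**The concern.** The primary objective is the safety of the cream as an adjunct to energy-based therapy. The schedule creates periods in which only the device, or mainly the cream, can explain a new event. None of the listed incidence tables reports by those periods, and none reports all drug-related events on their own.

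The SOC and PT tables do not close this gap, because SAP 6.2 counts a subject once per PT. Erythema is a named device effect (Protocol 4.5), and application site erythema was reported as a cream-related event in the long-term study (Protocol 4.3). If both are coded to the same PT, a subject with erythema after a session and again after the cream contributes one count, and the later event does not show in the incidence.

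At stake is whether the headline TEAE figure can say anything about the cream. The sample size in Protocol 8.2 rests on a study-drug-related rate, while the nearest listed SAP table mixes drug and device.

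**Working it through.** **1. The plan's own figure.** Protocol 8.2 takes p0 = 0.082 for study-drug-related events, margin 0.14, power 80% and alpha 5%, and reports N = 43. With the upper bound pU = 0.082 + 0.14 = 0.222:

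N = [(1.645·√(0.222·0.778) + 0.842·√(0.082·0.918)) / 0.14]² = 42.67, rounded up to 43.

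This matches, so the sample size is not in dispute here. The quantity it was built on is a drug-related rate.

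**2. How far the overall TEAE incidence responds to the cream.** Let q be the share of subjects with a device event per session (assumed, since the documents give none), c the share with a cream event, and let sessions and cream act independently. Then

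incidence = 1 − (1−q)²(1−c).

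Raising c from 8.2% to 22.2% moves it by (1−q)² × 14 points:

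| q per session | device only, 1−(1−q)² | c = 8.2% | c = 22.2% | shift (points) |
|---|---|---|---|---|
| 5% | 9.8% | 17.2% | 29.8% | 12.6 |
| 20% | 36.0% | 41.2% | 50.2% | 9.0 |
| 40% | 64.0% | 67.0% | 72.0% | 5.0 |
| 60% | 84.0% | 85.3% | 87.6% | 2.2 |

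For scale, 30/45 = 66.7% has an exact 95% CI of 51.0% to 80.0%. A 5-point shift cannot be seen against that.

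Independence matters. If the same subjects react at both sessions, the factor is (1−q) rather than (1−q)². At q = 40% the shift is then 0.60 × 14 = 8.4 points.

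**3. The pooled related-TEAE table.** Let Q be the share of subjects with a device-related event at either session, independent of a drug-related rate of 8.2%. Pooled incidence = 1 − 0.918(1−Q). It reaches 22.2% when Q = 1 − 0.778/0.918 = 15.3%, with no change in drug risk. At Q = 20% it is 26.6%. At N = 45 that is about 12/45 (26.7%, exact 95% CI 14.6% to 41.9%), where the drug-related row alone would be about 4/45 (8.9%, CI 2.5% to 21.2%).

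**4. What onset dates can and cannot do.** On the nominal schedule the four windows are Days 1–2, 3–28, 29–30 and 31–56: 2, 26, 2 and 26 days. A date alone places every event that starts on Days 2, 4–28, 30 and 32–55. It leaves open Days 1 and 29 (before or after the session) and Days 3 and 31 (before or after the cream). On Day 56 the order does not change the window. Day 1 matters further because SAP 6.2 divides pretreatment from treatment-emergent events at the session itself.

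**The case against.** **Counting from the first session is not an error.** Protocol 7.1.2.1 defines TEAEs relative to the study treatments, and the objective concerns the combination. This stands, and the overall count should stay.

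**A reader might infer that the separation is never used.** The documents do not support that. Causality is graded on the time relationship to study drug, and the investigator judges device reactions before cream is applied. Protocol 4.5 and 5.6.7 also give the spacing other purposes: limiting interaction, alerting the physician, and keeping the cream off recovering skin. SAP 6.2 and 6.3 refer to analyses by visit or timepoint, and SAP section 6 defines incidence over a period. Those analyses are left undefined, are not in the lists of tables, and are to carry no CI. The mock-up shells mentioned in SAP 2.1 were not available.

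**A reader might infer that date-only onset is what prevents the separation.** It is not: dates place most onsets. The cause is that no onset-window table is specified. The absence of a time field is itself inferred from the protocol's list of AE items, because the eCRF is not among the documents.

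**A reader might infer that laser reactions will dominate the headline figure.** That depends on an assumed rate. At q = 5% the shift is 12.6 of a possible 14 points. Some expected erythema may also never be recorded as an AE, since Protocol 7.1.2.1 exempts anticipated fluctuations of the disease and worsening captured by efficacy assessments.

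**Other outputs help.** All TEAEs are listed. Dermal tolerability is reported by visit and timepoint, with predose, 1-hour and 6-hour assessments on Days 3, 31 and 56. This is a real mitigation, but only for dryness, scaling, stinging/burning and pruritus.

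**Conclusion.** The point holds as a gap in specified reporting. No listed TEAE or SAE table uses the onset windows that the schedule creates. Drug-related and device-related TEAEs appear together in the only table that covers all related events. The overall incidence may therefore be diluted by device reactions: a 14-point rise in the cream event rate shows as 12.6 points at q = 5% and 2.2 points at q = 60%, under independence between sessions and cream. These sizes illustrate the mechanism and do not predict the result, because the documents contain no device-event rate and correlated sessions would weaken the dilution.

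Onset dates are sufficient for most of the split. They fall short only on the session and first-dose days, which are also the days when immediate reactions would begin.

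**What to change.** 1. Keep the overall TEAE and SAE incidence as planned.
2. Add to SAP 6.2 and 6.3 a unique-subject table by onset window, with the Clopper-Pearson 95% CIs that SAP section 6 already specifies. The windows are session 1 to first cream, first cream to session 2, session 2 to cream restart, and restart to exit. Define them from each subject's actual treatment dates, since the Day 29 visit may move by 3 days. State the unequal lengths in the table, so that the raw percentages are not read as comparable rates.
3. Report study-drug-related and energy-therapy-related TEAEs separately as well as pooled. This requires recording relationship to energy-based therapy, which the existing pooled and device-specific tables already presuppose.
4. On the session and first-dose days (nominally Days 1, 3, 29 and 31), record whether onset was before or after the session or application.
5. Either define the by-visit/timepoint TEAE analyses or remove the reference to them.

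The cost is one more AE table for each event class, the related-TEAE split and minor eCRF fields. No clinical procedure changes. The onset-window table uses dates already collected, so it remains feasible for most events even if the eCRF can no longer be changed. Window-level CIs will be wide at N = 45, and the table should be read as descriptive.

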### Assessment of Causality

Every effort will be made by the investigator to assess the relationship of the AE, if any, to the study drug. Causality should be assessed using the categories presented in the following table:

Unrelated:	Clinical event with an incompatible time relationship to study drug administration, and that could be explained by underlying disease or other drugs or chemicals or is incontrovertibly not related to the study drug.
Unlikely:	Clinical event whose time relationship to study drug administration makes a causal connection improbable, but that could plausibly be explained by underlying disease or other drugs or chemicals.
Possible:	Clinical event with a reasonable time relationship to study drug administration, but that could also be explained by concurrent disease or other drugs or chemicals.
Probable:	Clinical event with a reasonable time relationship to study drug administration, and is unlikely to be attributed to concurrent disease or other drugs or chemicals.
Very Likely/Certain:	Clinical event with plausible time relationship to study drug administration, and that cannot be explained by concurrent disease or other drugs or chemicals.

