### **Action Taken**

The investigator will describe the action taken in the appropriate section of the eCRF, as follows:

- Study drug stopped
- Study drug temporarily interrupted
- Energy-based therapy stopped
- Energy-based therapy temporarily interrupted
- Concomitant medication

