# 8.1.2 Demographic and Other Baseline Characteristics

The number of subjects in each of the analyzed study populations will be described. Subjects who discontinue study drug or are removed from the study prematurely will also be reported. Reasons for study drug and/or energy-based therapy discontinuation, and time of withdrawal from the study will be described.

Subject characteristics at entry into the study will be summarized in frequency tables and descriptive statistics will be provided for quantitative variables.

Concomitant medications will be coded by means of the World Health Organization Drug Dictionary (WHODrug) dictionary into Anatomical Therapeutic Chemical (ATC) classification codes. The type and timing of use of specific concomitant medications will be listed and summarized. The type and duration of pre-study use will be described on the safety population. The type, dose, schedule, duration of use, dose modifications, dose omissions, and reasons for deviations from initial therapy will be described.

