3.2 Disposition and Exit Status

Reasons for exclusion from safety population will summarized and will be listed for the enrolled population. Subject disposition will be listed for the enrolled population.

4. Demographics and Baseline Characteristics

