6.3 Serious Adverse Events

A serious adverse event (SAE) is any AE occurring at any dose that results in any of the following outcomes: death, a life-threatening AE, inpatient hospitalization or prolongation of existing hospitalization, a persistent or significant disability/incapacity, or a congenital anomaly/birth defect. Important medical events that may not result in death, be life-threatening, or require hospitalization may be considered a SAE when, based upon appropriate medical judgment, they may jeopardize the patient and may require medical or surgical intervention to prevent one of the outcomes listed in this definition. Allergan considers all cancer AEs as SAEs. In addition, an abortion (spontaneous or non-spontaneous) is also considered a SAE. Any pre-planned surgery or procedure should be clearly documented in the source documents at the center by the medically qualified investigator at the time of the patient's entry into the study. If it has not been documented at the time of the patient's entry into the study, then it should be documented as a SAE and reported to Allergan.

If an unexpected AE is serious and suspected, it is a suspected "unexpected" serious adverse reactions (SUSAR). See Section of 7.1.2.1.2 of the Protocol for details, such as what is considered as "unexpected".

An overall summary of frequency count and the binomial incidence proportion with the associated 95% CIs will be presented to describe the incidents of treatment emergent SAEs. Note that 95% CIs of the binomial incidence proportion will be presented for the overall summary analyses of SAE, but not for the by-visit/timepoint analyses. Percentages and corresponding 95% CIs will be displayed to 1 decimal place.

The incidence of all treatment-emergent SAEs by SOC and PT within SOC will be presented for the following categories:

- Any SAE
- Any SAE related to energy-based therapy and leading to discontinuation of study

medication

- Any SAE related to treatment (i.e., study medication or energy-based therapy or both)
- Any SAE by maximum severity
- Any SUSAR

The following listings will be provided:

- Listing of subjects who died
- Listing of subjects with treatment-emergent SAEs
- Listing of subjects with treatment-emergent SAEs related to energy-based therapy and leading to discontinuation of study medication
- Listing of patients with treatment-emergent SAEs leading to discontinuation of

treatment

• Listing of patients with any SUSAR

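### The only tabulated discontinuation category requires attribution to the energy device, so stops attributed solely to the cream are listed but get no rate

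*SAP*

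**What the plan says.** The primary objective (Protocol 4.6, SAP 1.1.2) is the safety and tolerability of the cream as an adjunct to energy-based therapy.

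SAP 6.2 names five categories for incidence by system organ class and preferred term: any TEAE, related TEAEs, TEAEs by maximum severity, pretreatment events, and one category with a discontinuation condition, "Any TEAE related to energy-based therapy and leading to discontinuation of study medication". The related category pools the two treatments: "Any TEAE related to treatment (i.e., study medication or energy-based therapy or both". SAP 6.3 has the matching serious-event category, "Any SAE related to energy-based therapy and leading to discontinuation of study" (the last word, medication, falls on the next line). Discontinuation for events of any attribution is covered by "Listing of patients with TEAEs leading to discontinuation of treatment", and SAP 6.3 has a similar listing for serious events.

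Protocol 7.1.2.1, under Action Taken, has the eCRF record whether the drug was stopped, "Study drug temporarily interrupted", and whether energy-based therapy was stopped or interrupted. Under Assessment of Causality the investigator is asked "to assess the relationship of the AE, if any, to the study drug". The SAP 6.2 relationship scale is likewise to study drug.

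On disposition, Protocol 8.1.2 states: "Reasons for study drug and/or energy-based therapy discontinuation, and time of withdrawal from the study will be described". SAP 3.2 summarises reasons for exclusion from the safety population and adds: "Subject disposition will be listed for the enrolled population".

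**The concern.** In a single-arm tolerability study, readers look for how many subjects stopped or interrupted the product because of an adverse event. Here the only planned rate of that kind depends on the event being blamed, at least in part, on the device. A subject who stops the cream for an application-site reaction attributed to the cream alone does not contribute to it. Interruption is foreseeable, since Protocol 5.6.1 and 5.6.7 both anticipate delaying the cream after a device reaction, yet no adverse event table counts it.

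The existing row also depends on an attribution that neither document defines. Without a stated assessment of relatedness to the energy therapy, sites may judge it differently or not at all.

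**Working it through.** The documents give no discontinuation rate to reproduce. The check is a comparison of what is collected with what is tabulated, followed by an illustration.

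**Step 1. Where each kind of event is reported (SAP 6.2; SAP 6.3 follows the same pattern).**

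| Action taken for the event | Attribution | Incidence row with that action | Named listing for that action |
|---|---|---|---|
| Cream stopped | Device only | Yes | Yes |
| Cream stopped | Cream and device | Yes | Yes |
| Cream stopped | Cream only | No | Yes |
| Cream stopped | Neither | No | Yes |
| Cream interrupted | Any | No | No |
| Energy therapy stopped | Any | No | Possibly: the listing does not split treatment into cream and device |
| Energy therapy interrupted | Any | No | No |

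A cream-only event is still counted under any TEAE and under the pooled related category, but neither has a discontinuation condition and the pooled category has no cream-only split. All events also go into the by-subject listing. Discontinuation categories tabulated: two (one for TEAEs, one for SAEs), both requiring relation to the device. Categories that count stops or interruptions attributed solely to the cream: none.

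**Step 2. Source of the device attribution.** The scale in Protocol 7.1.2.1 is defined by the time relationship to study drug administration. The SAP 6.2 scale is relationship to study drug. Neither has a counterpart for energy therapy, although the device row and the pooled related row both need one.

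**Step 3. What the missing row could show.** The denominator is N = 43, the required sample size in Protocol 8.2. That figure reproduces with p0 = 0.082, margin 0.14, and null variance taken at 0.082 + 0.14 = 0.222: ((1.645 × √(0.222 × 0.778) + 0.842 × √(0.082 × 0.918)) / 0.14)² = 42.67, rounded up to 43. The point does not depend on it.

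The interval is Clopper-Pearson, the method in SAP Section 6: lower limit = Beta quantile 0.025 with parameters (x, N − x + 1); upper limit = Beta quantile 0.975 with parameters (x + 1, N − x). For x = 0 the lower limit is 0 and the upper limit is 1 − 0.025^(1/43) = 8.2%.

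The counts x are assumptions:

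| Subjects stopping for a cream-only event | N = 43 | N = 45 (planned enrolment) |
|---|---|---|
| 0 | 0% (0 to 8.2) | 0% (0 to 7.9) |
| 1 | 2.3% (0.1 to 12.3) | 2.2% (0.1 to 11.8) |
| 2 | 4.7% (0.6 to 15.8) | 4.4% (0.5 to 15.1) |
| 3 | 7.0% (1.5 to 19.1) | 6.7% (1.4 to 18.3) |
| 4 | 9.3% (2.6 to 22.1) | 8.9% (2.5 to 21.2) |

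In every line, if no stop was attributed to the device, the row the SAP does plan reads 0.

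**Step 4. Plausibility of the counts.** Protocol 4.3 reports any treatment-related TEAE in 36/440 = 8.2% over 52 weeks of cream alone. At that rate 0.082 × 43 = 3.5 subjects would have a related event of any kind, and only some of them would stop. Four stops is therefore a high value on that experience. The rate with energy therapy added is unknown.

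**The case against.** The best defence is that nothing is hidden. An all-attribution listing of discontinuations is planned, and with about 45 subjects anyone can count it. Discontinuation is not a primary endpoint: Protocol 5.1 names TEAE and SAE incidence and one-grade worsening in dermal tolerability and telangiectasia, all reported as proportions. The device row also has a purpose, because Protocol 5.6.1 asks the investigator to judge whether a device reaction makes continued cream use a risk. All of this stands. It limits the seriousness of the point and is a reason to keep the row, but a listing gives no incidence or interval.

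Several stronger readings are tempting, and the documents do not support them:

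- A reader might infer that a discontinuation rate appears only when the cream was not blamed. The row requires relation to the device but does not exclude relation to the cream, so events attributed to both are counted.
- A reader might infer that the SAP withdrew the Protocol 8.1.2 commitment without declaring it. SAP Section 1 says protocol content is generally not restated, so silence does not clearly withdraw it. It does leave the description without a specified output.
- A reader might infer that interruptions leave no trace. SAP 6.1 summarises treatment duration, days of cream use and number of energy sessions. What is missing is the cause.
- A reader might infer that no device-causality data exist. The eCRF and table shells are not available, and the documentation list in Protocol 7.1.2.1 asks for a causal relationship without limiting it to the drug. The supported statement is that no assessment is defined. For the same reason, the rows of the overall TEAE summary in SAP 6.2 cannot be checked.

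**Conclusion.** The point holds as a reporting gap that should be closed. The only tabulated discontinuation categories require relation to energy therapy, so stops attributed solely to the cream, or to neither treatment, have no rate, and the other recorded actions have no adverse event table. No primary endpoint estimate changes and no data are lost.

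The size depends on an unknown count. For 0 to 4 cream-only stops among 43 subjects the unreported rate runs from 0% to 9.3%, with an upper confidence limit from 8.2% to 22.1%. A reader might take a printed 0% in the device row to mean that nobody stopped the cream for poor tolerability. The row label does not say that, but no other rate would correct the impression.

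The conclusion rests on the categories named in SAP 6.2 and 6.3 being the full set, and on the table shells not adding others.

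**What to change.** 1. In SAP 6.2 and 6.3 keep the device-related row and add rows, regardless of attribution, from the Action Taken field: events leading to study drug stopped, study drug interrupted, energy therapy stopped, and energy therapy interrupted. Give n, % and the Clopper-Pearson 95% CI for each, split by attribution to cream, device, both or neither.
2. In Protocol 7.1.2.1 and the eCRF, record causality separately for study drug and for energy therapy, and have SAP 6.2 refer to both items.
3. In SAP 3.2, add a summary of reasons for discontinuing study drug and energy therapy and of time of withdrawal, so that Protocol 8.1.2 has an output.

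The cost is SAP wording, a few table rows and one extra eCRF field. Many split cells will be small or zero in a study of this size, and the reported discontinuation figure may be less favourable. Clinical management does not change.
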